1.4 STUDY RATIONALE AND BENEFIT-RISK ASSESSMENT

This open-label extension (OLE) study will evaluate the long-term safety and tolerability of ITV injections of FHTR2163 in patients with GA secondary to AMD. Currently, there are no approved treatments to slow or stop the progression of GA secondary to AMD and associated vision loss. FHTR2163 is a first-in-class inhibitor of HtrA1 in clinical development, and as such there are no published data on the clinical benefit of this mechanism for the treatment of GA secondary to AMD.

The clinical experience with FHTR2163 consists of data from the Phase I first-in-human study (GR39821) and emerging data from the ongoing Phase II study (GR40973), as described in Section 1.3.2 and the FHTR2163 Investigator's Brochure. Given the early phase of development, the safety profile of FHTR2163 in humans is not fully understood at this time. This OLE study will complement the Phase II parent study (GR40973), permitting the evaluation of long-term safety and tolerability of FHTR2163 in patients who have completed that study. In addition, this OLE study will provide an opportunity for eligible patients undergoing sham injections in Study GR40973 to receive FHTR2163.

Data from completed nonclinical pharmacology, PK, and toxicology studies, data from the completed Phase I study (GR39821), and emerging safety data from the ongoing Phase II study (GR40973) support the continued clinical development of FHTR2163 in patients with GA secondary to AMD (see Sections 1.3.1 and 1.3.2). There are no identified risks for FHTR2163 to date. Potential risks are described in Section 5.1.1. Several measures are being taken in this study to mitigate possible safety concerns, including strict inclusion and exclusion criteria (see Section 4.1), physical examinations (see Section 4.5.2), regular ocular assessments (see Section 4.5.4), and regular ocular imaging (see Section 4.5.5). Because of the high unmet medical need for new treatments for GA secondary to AMD and the safety profile of FHTR2163 observed in both nonclinical and clinical studies to date, the benefit–risk of FHTR2163 is favorable and supportive of its continued use in this OLE study.

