3.1 DESCRIPTION OF THE STUDY

Study GR42558 is a multicenter, OLE study to evaluate the long-term safety and tolerability of ITV injections of FHTR2163 in patients with GA who completed the parent study. Patients who discontinued from the parent study or discontinued from study treatment prior to completion of the final (Week 76) visit are not eligible for enrollment in this OLE study. Approximately 360 patients are expected to participate in the OLE study.

Patients who consent to participate in the OLE study will be screened for eligibility upon completion of the parent study (i.e., Week 76 visit). The Week 76 visit will serve as the final visit for the parent study and the first (Day 1) visit for the OLE study (i.e., the two visits are to be conducted on the same day), and all Week 76 assessments must be completed prior to conducting Day 1 assessments. If all assessments for the Day 1 visit cannot be completed on the same day as the Week 76 visit, patients may return to the clinic within 28 days to complete the Day 1 visit. If a patient is not able to complete the Day 1 visit within 28 days, the investigator must contact the Medical Monitor for further discussion prior to scheduling the Day 1 visit.

Patients will receive 20 mg of FHTR2163 or 10 mg of FHTR2163 by ITV injection in the same eye selected for injections in the parent study (referred to as the "study eye") Q4W or Q8W for approximately 144 weeks. Dosing frequency will remain consistent with each patient's original dosing schedule in the parent study (i.e., Q4W or Q8W). Upon implementation of protocol Version 4, all eligible patients in the sham control arms of the parent study that are newly enrolling in the OLE study will receive 10 mg of FHTR2163 (Q4W or Q8W; see Figure 1). Patients currently enrolled in the OLE study (i.e. enrolled prior to implementation of protocol Version 4) will continue receiving their current dosing regimen for the remainder of the study.

Figure 1 presents an overview of the study design. Schedules of activities are provided in Appendix 1 and Appendix 2.

FHTR2163—Genentech, Inc. 23/Protocol GR42558, Version 4

Figure 1 Study Schema

Q4W = every 4 weeks; Q8W = every 8 weeks.

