4.5.2 Physical Examinations

A targeted physical examination should include an evaluation of the head, eyes, ears, nose, throat, and cranial nerves. The patient's weight will be measured as well. Any abnormality identified at Day 1 (screening) should be recorded on the General Medical History and Baseline Conditions eCRF. If any abnormalities are noted during the study, the patient may be referred to their primary care physician or an appropriate specialist for further evaluation. Changes from baseline abnormalities should be recorded in patient notes. New or worsened clinically significant abnormalities should be recorded as adverse events on the Adverse Event eCRF.

4.5.3 Vital Signs

Vital signs will include measurements of respiratory rate, pulse rate, and systolic and diastolic blood pressure while the patient is in a seated position after resting for 5 minutes, and temperature.

4.5.4 Ocular Assessments

Ocular assessments will include the following, to be performed on both eyes (with the exception of post-injection safety assessments) at timepoints specified in the schedules of activities (see Appendix 1 and Appendix 2). A detailed examination to evaluate for signs of intraocular inflammation (IOI) should be performed prior to any study drug administration.

• BCVA assessment as determined by Early Treatment Diabetic Retinopathy Study (ETDRS) chart at a starting distance of 4 m

Perform assessment prior to dilating eyes. Refer to Appendix 3 and the Clinical Edge Visual Acuity Certification Procedure Manual for more information on BCVA assessments.

• Low-luminance BCVA assessment as determined by ETDRS chart at a starting distance of 4 m under low-luminance conditions

Perform assessment prior to dilating eyes. Refer to Appendix 4 and the Clinical Edge Visual Acuity Certification Procedure Manual for more information on low-luminance BCVA assessments.

• Pre-injection IOP measurement

Perform assessment prior to dilating eyes. The method of IOP measurement used for a patient must remain consistent throughout the study.

• Slit-lamp examination

Perform examination prior to dilating eyes. Refer to Appendix 5 for grading scales for anterior chamber flare or cells and vitreous cells.

- Dilated binocular indirect high-magnification ophthalmoscopy examination
- Finger-counting test, followed by hand motion and light perception tests when necessary, performed for the study eye within 15 minutes after study drug injection (see Appendix 6)

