5.2 SAFETY PARAMETERS AND DEFINITIONS

Safety assessments will consist of monitoring and recording adverse events, including serious adverse events and adverse events of special interest, performing protocol-specified safety laboratory assessments, measuring protocol-specified vital signs, and conducting other protocol-specified tests that are deemed critical to the safety evaluation of the study.

Certain types of events require immediate reporting to the Sponsor, as outlined in Section 5.4.

5.2.1 Adverse Events

According to the ICH guideline for Good Clinical Practice, an adverse event is any untoward medical occurrence in a clinical investigation subject administered a pharmaceutical product, regardless of causal attribution. An adverse event can therefore be any of the following:

- Any unfavorable and unintended sign (including an abnormal laboratory finding), symptom, or disease temporally associated with the use of a medicinal product, whether or not considered related to the medicinal product
- Any new disease or exacerbation of an existing disease (a worsening in the character, frequency, or severity of a known condition) (see Sections 5.3.5.11 and 5.3.5.12 for more information)
- Recurrence of an intermittent medical condition (e.g., headache) not present at baseline
- Any deterioration in a laboratory value or other clinical test (e.g., ECG, X-ray) that is associated with symptoms or leads to a change in study treatment or concomitant treatment or discontinuation from study drug
- Adverse events that are related to a protocol-mandated intervention, including those that occur prior to assignment of study treatment (e.g., screening invasive procedures such as biopsies)

5.2.2 Serious Adverse Events (Immediately Reportable to the Sponsor)

A serious adverse event is any adverse event that meets any of the following criteria:

- Is fatal (i.e., the adverse event actually causes or leads to death)
- Is life threatening (i.e., the adverse event, in the view of the investigator, places the patient at immediate risk of death)

This does not include any adverse event that, had it occurred in a more severe form or was allowed to continue, might have caused death.

- Requires or prolongs inpatient hospitalization (see Section 5.3.5.13)
- Results in persistent or significant disability/incapacity (i.e., the adverse event results in substantial disruption of the patient's ability to conduct normal life functions)

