6.1 DETERMINATION OF SAMPLE SIZE

This study is open to all patients who completed FHTR2163 treatment and follow-up through the final (Week 76) visit of the parent study and meet the eligibility criteria outlined in Sections 4.1.1 and 4.1.2). Accordingly, the sample size for this study is not based on a formal sample size calculation.

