Appendix 1 Schedule of Activities for Q4W Arms Weeks 100–148

						Wee	k (±5 c	lays)							
					Treat	ment F	Period	Visits					FU Call		
	100	104	108	112	116	120	124	128	132	136	140	144	148	UV	ET a
Physical examination ^b														Хc	х
Vital signs ^d														Хc	х
Hematology, coagulation, lipids, serum chemistry (central laboratory) ^e												x		Хc	x
Urine pregnancy test ^f	х	х	х	х	х	х	х	х	х	х	х	х		Xc	
Plasma sample for biomarkers												х		X c	х
Serum ADA sample ^g												х		X ^{c, g}	х
Serum PK sample for drug concentration ^g												x		X ^{c, g}	х
BCVA testing (starting at 4 m) ^h	х	х	х	х	х	х	х	х	х	х	х	х		х	х
LL BCVA testing (starting at 4 m) ^h						х						х		Хc	х
IOP measurement ^h	х	х	х	х	х	х	х	х	х	х	х	х		х	х
Slit-lamp examination ⁱ	х	х	х	х	х	х	х	х	х	х	х	х		х	х
Aqueous humor sample ^j												х		Хc	
Dilated binocular indirect ophthalmoscopy	x	x	x	x	x	x	x	x	x	х	x	x		Хc	х
FAF ^k						х						х		Хc	х
SD-OCT ^k		х		х		х		х		х		х		X ^{c, g}	х
OCT-A ^{k,}						х						х		Xc	х
NI images ^k						х						х		Xc	х

FHTR2163—Genentech, Inc. 81/Protocol GR42558, Version 4

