Appendix 2 Schedule of Activities for Q8W Arms

	Day	y 1 ª	Week (±5 days)																				
										Trea	tmen	t Peri	iod Vi	isits							FU Call		
	PS♭	OLE	8	16	24	32	40	48	56	64	72	80	88	96	104	112	120	128	136	144	148	UV	ET℃
Written informed consent		X d																					
Review inclusion and exclusion criteria		x																					
Medical and surgical history, including tobacco history	Ex																						
Review medical and surgical history including tobacco history		x																					
Demographic information	Ex																						
Physical examination ^e		х																				Хţ	х
Vital signs ^g		х																				Хf	х
Hematology, coagulation, lipids, serum chemistry (central laboratory) ^h	Ex							x						x						x		Хţ	x
Urine pregnancy test ⁱ		х	х	х	х	х	х	х	х	х	х	х	х	х	х	х	х	х	х	х		X f	
Enrollment (IWRS)		х																					
Plasma sample for biomarkers	Ex							х						х						х		X f	х
Serum ADA sample ^j	Ex				x			х			x			х						х		X ^{f, j}	х
Serum PK sample for drug concentration ^{j, n}	Ex				x			х			x			х						x		x ^{f, j}	x
BCVA testing (starting at 4 m) ^k	Ex		х	х	х	х	х	х	х	х	х	х	х	х	x	х	х	х	х	х		х	х
LL BCVA testing (starting at 4 m) ^k	Ex				x			x			х			x			x			x		Хţ	x

FHTR2163—Genentech, Inc. 85/Protocol GR42558, Version 4

	Dav	/1ª									We	ek (±	5 dav	/s)									
										Trea	tmen	t Peri	iod Vi	sits							FU Call		
	PS ^b	OLE	8	16	24	32	40	48	56	64	72	80	88	96	104	112	120	128	136	144	148	UV	ET
IOP measurement ^k	Ex		х	х	х	х	х	х	х	х	х	х	х	х	х	х	х	х	х	х		х	x
Slit-lamp examination ¹	Ex		х	х	х	х	х	х	х	х	х	х	х	х	х	х	х	х	х	х		х	x
Aqueous humor sample ^{m, n}	Ex n				x			х			x			х						х		Хţ	
Dilated binocular indirect ophthalmoscopy	Ex		x	x	x	x	x	x	x	x	x	x	x	x	x	x	x	x	x	x		X f	x
FAF°	Ex				х			х			х			х			х			х		X f	x
SD-OCT °		х	х	х	х	х	х	х	х	х	х	х	х	х	х	х	х	х	х	х		X ^{f, j}	x
OCT-A ^{o, p}	Ex				х			х			х			х			х			х		X f	x
NI ⁿ	Ex				х			х			х			х			х			х		X f	x
Color fundus photography ^o	Ex							х						х						х		X ^{f, j}	х
Administration of study drug to study eye ^q		x	x	x	x	x	x	x	x	x	x	x	x	x	x	x	x	x	x	x			
Post-treatment finger counting and IOP measurement ^r		x	x	x	x	x	x	x	x	x	x	x	x	x	x	x	x	x	x	x			
Concomitant medications ^s	Ex		х	х	х	х	х	х	х	х	х	х	х	х	х	х	х	х	х	х		х	x
Adverse events ^t	Ex		х	х	х	х	х	х	х	х	х	х	х	х	х	х	х	х	х	х	х	х	x
Concurrent ocular procedures ^u	Ex		х	х	х	х	х	х	х	х	х	х	х	х	х	х	х	х	х	х		х	x
Follow-up call ^v		х	х	х	х	х	х	х	х	х	х	х	х	х	х	х	х	х	х	х			

С

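### After Day 1, vital signs and the physical examination are scheduled only at early termination, so completers have no scheduled post-baseline value, even at Week 144

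*Combined protocol and SAP*

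**What the plan says.** Several sections of the protocol treat the physical examination and vital signs as working safety measures:

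- Section 1.4 states: "Several measures are being taken in this study to mitigate possible safety concerns, including strict inclusion and exclusion criteria (see Section 4.1), physical examinations".
- Section 4.5.2 defines a targeted examination (head, eyes, ears, nose, throat, cranial nerves, plus weight) and adds: "New or worsened clinically significant abnormalities should be recorded as adverse events on the Adverse Event eCRF".
- Section 5.2 includes "measuring protocol-specified vital signs" among the safety assessments.
- Section 5.3.5.8 sets out when a vital-sign abnormality is an adverse event, and how to record one that is seen again at later visits.

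The schedules provide little for these rules to act on. In Appendix 1 for Weeks 100–148, the row "Physical examination ^b" is marked only for unscheduled visits and early termination. In Appendix 2, the row "Physical examination ^e" is marked only at Day 1, unscheduled visits and early termination. The first part of Appendix 1 (Day 1–Week 96) follows the same pattern, as do the vital-signs rows throughout. A footnote makes the unscheduled-visit mark conditional on clinical need. Under Section 4.6.2, only patients who leave the study early have the early termination visit.

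In the analysis plan, Section 6.3 names vital signs as baseline data. Section 6.4 lists adverse events, ocular assessments, laboratory evaluations, ocular imaging and immunogenicity. It lists neither post-baseline vital signs nor physical examination findings.

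**The concern.** The text counts on assessments that the schedules do not provide for patients who stay. Treatment runs "Q4W or Q8W for approximately 144 weeks", and a patient who attends every visit to the end is never due a second blood pressure, pulse, weight or cranial-nerve examination. A patient who leaves early is due one.

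Systemic adverse events are one of the two components of the primary safety endpoint. Those with symptoms can be picked up by questioning. A silent rise in blood pressure or a subtle neurological sign has to be looked for. Appendix 14 shows this: its Grade 1 hypertension is a transient rise of more than 20 mm with no treatment, which may go unseen unless pressure is measured. At the end of a long-term safety study, the sponsor would have baseline vital signs and no systematically collected follow-up in completers. The only scheduled post-baseline values would come from patients who left.

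**Working it through.** No power, alpha or effect-size figure bears on this. Section 6.1 says that "the sample size for this study is not based on a formal sample size calculation". The check is a count of scheduled assessments.

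**Inputs.** Visit columns and row marks come from Appendices 1 and 2. Planned enrolment comes from Section 3.1: "Approximately 360 patients are expected to participate in the OLE study".

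**Treatment visits after Day 1.**
- Q4W, Weeks 4 to 144 in steps of 4: 144 / 4 = 36 visits. With Day 1, 36 + 1 = 37 injections.
- Q8W, Weeks 8 to 144 in steps of 8: 144 / 8 = 18 visits. With Day 1, 18 + 1 = 19 injections.
- Week 148 is a telephone call in both schedules, so nothing can be measured there.

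**Scheduled assessments after Day 1.**

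| Assessment | Completer, Q4W | Completer, Q8W | Early termination visit |
|---|---|---|---|
| Physical examination | 0 of 36 | 0 of 18 | 1 |
| Vital signs | 0 of 36 | 0 of 18 | 1 |
| Central laboratory tests | 3 (Weeks 48, 96, 144) | 3 (Weeks 48, 96, 144) | 1 |

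**Are the blanks real?** Each row was matched cell by cell to its column headings. Cells and columns agree in all three tables: 28 and 28 for Q4W to Week 96, 15 and 15 for Q4W from Week 100, and 23 and 23 for Q8W. The laboratory row, read the same way, falls at Weeks 48, 96 and 144. The blanks are therefore not a shift in the extracted tables.

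**What is covered elsewhere?** BCVA, IOP, slit-lamp examination and ophthalmoscopy are scheduled at every treatment visit after Day 1, so the eye part of the targeted examination is not missing. What remains is weight, the head, ear, nose, throat and cranial-nerve examination, and the vital signs listed in Section 4.5.3.

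**Timing of the one scheduled value.** Section 4.6.2 places early termination at least 30 days after the final dose. Section 5.3.1 ends the reporting of all adverse events 28 days after it. Since 30 > 28, a non-serious abnormality that first arises at that visit falls outside full reporting. Week 144 is a dosing visit, and the schedules require assessments before the injection. A measurement there would fall inside the reporting window for a patient still on treatment.

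**The case against.** A fair defence has four parts, and much of it stands.

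First, the wording can be reconciled. Section 1.4 calls the ocular assessments and imaging regular but does not say so of physical examinations. Section 5.2 refers to whatever vital signs the protocol specifies, and Day 1, unscheduled and early termination visits satisfy that. The rules in Sections 4.5.2 and 5.3.5.8 govern recording and set no frequency. This is right as far as it goes: the text is not in flat contradiction with the schedules. It still relies on a source of findings that is not scheduled for completers.

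Second, sparse systemic monitoring can be defended for this drug. Section 5.1.1.2 does not anticipate systemic effects, reports mean peak serum levels below 0.2 μg/mL, and considers signs of the hereditary HtrA1-deficiency disease very improbable. Section 1.3.1 reports no cardiovascular finding in animals. This stands, and the case for the change is routine reassurance, not a suspected hazard.

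Third, systemic events are sought in everyone: at each contact, by a call after each treatment visit, through concomitant-medication review, and by laboratory tests at three visits. This stands for symptomatic events and laboratory abnormalities. It does not reach silent changes in vital signs or on examination.

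Fourth, the study is non-randomized and all patients receive active drug, so drift in blood pressure would have no untreated comparator. That limits interpretation of a summary but does not remove its descriptive value.

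**Conclusion.** The point holds as a gap in data collection. A completer has 0 scheduled post-baseline physical examinations or vital signs over 144 weeks, and an early leaver has 1. The gap is confined to weight, the non-eye examination and vital signs. The count rests on the schedules alone and needs no assumption. It is a cheap improvement to the plan, not a flaw that threatens its conclusions.

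A reader might infer more, and the documents do not support it:

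- *That completers cannot have these assessments at all.* They can, at an unscheduled visit with a clinical reason. Those values are selected by indication, so they are no substitute for routine data.
- *That the primary analysis is biased because detection depends on leaving.* Sections 6.3 and 6.4 plan no post-baseline vital-sign comparison. The early termination value falls after full adverse event reporting has closed, which limits any extra capture of events in leavers. Section 4.6.1 urges patients who stop treatment to remain in the study, so stopping for an adverse event does not in itself lead to early termination.
- *That the number of patients affected can be stated.* The documents give no dropout rate. If 20–40% of 360 left early (an assumption), 72–144 could have an early termination value and 216–288 would have none. Even 72–144 would be an upper bound at those rates, because patients lost to follow-up or withdrawing consent may not attend.
- *That a cerebrovascular risk is going unmonitored.* Section 5.1.1.2 raises that disease in order to explain why it is not expected.

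**What to change.** In Appendices 1 and 2, mark vital signs and the targeted physical examination at Week 144, before dosing. Completers would then have an end-of-study value, as they already do for laboratory tests. Weeks 48 and 96, where laboratory samples are already drawn, are optional additions.

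In Section 6.4, add a descriptive summary of change in vital signs from OLE baseline. Report Week 144 and early termination separately, because the first is taken on a dosing day and the second at least 30 days after the last dose.

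If the omission is deliberate, say so and align Sections 1.4, 4.5.2, 5.2 and 5.3.5.8 with the schedules.

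The cost is two rows in each schedule, one line in Section 6.4, and a few minutes at an existing visit. No new visit, staff or equipment is needed.

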4.5.5 Ocular Imaging

Ocular images to be obtained during the study include the following:

- Digital color fundus photographs (CFPs) of both eyes (see Appendix 7)
- FAF images of both eyes (see Appendix 8)
- Near infrared (NI) images of both eyes (see Appendix 9)
- SD-OCT images of both eyes (see Appendix 10)
- OCT-A images of both eyes (for sites with OCT-A capabilities) (see Appendix 11)

Both eyes will be dilated prior to ocular imaging. Additional details on obtaining these images are included in the Central Reading Center Manual.

4.5.6 Follow-Up Calls

After each study treatment visit, the site must contact the patient 14 (± 5) days after each treatment visit and query for adverse events; particularly any signs or symptoms of decreased visual acuity and/or inflammation (e.g., painful red eye, floaters, scotoma, pain). If the patient reports any concerning signs and/or symptoms, the patient must be evaluated by the investigator as soon as possible.

4.5.7 Laboratory, Biomarker, and Other Biological Samples

Fasting is not required prior to specimen collection. The specimens will be sent to a central laboratory. The central laboratory will either perform the analysis or send the samples to the Sponsor or a designee for analysis and/or storage.

Samples will be collected for the following analyses:

- Hematology: WBC count, RBC count, hemoglobin, hematocrit, platelet count, and differential count (neutrophils, eosinophils, basophils, monocytes, lymphocytes, and other cells)
- Chemistry panel (serum): sodium, potassium, glucose, BUN or urea, creatinine, total protein, albumin, total and direct bilirubin, ALP, ALT, and AST
- Coagulation: INR, aPTT, and PT
- Lipids: cholesterol, LDL cholesterol, HDL cholesterol, and triglycerides
- Pregnancy test

All women of childbearing potential will have a urine pregnancy test prior to each study drug injection. If a urine pregnancy test is positive, it must be confirmed by a serum pregnancy test.

- PK analysis (serum and aqueous humor)
- Immunogenicity analysis (serum)
- Exploratory biomarker research (plasma and aqueous humor)

Exploratory biomarker research may include, but will not be limited to, cleaved DKK3 and other biomarkers associated with HtrA1, GA, and/or AMD. Research may involve extraction of cell-free DNA.

For sampling procedures, storage conditions, and shipment instructions, see the laboratory manual.

Unless the patient gives specific consent for his or her leftover samples to be stored for optional exploratory research (see Section 4.5.8), biological samples will be destroyed no later than the time of completion of the final Clinical Study Report, with the following exceptions:

- Serum and aqueous humor samples collected for PK or immunogenicity analysis may be needed for additional immunogenicity characterization and for PK or immunogenicity assay development and validation; therefore, these samples will be destroyed no later than 5 years after the final Clinical Study Report has been completed.
- Blood and aqueous humor samples collected for biomarker research and biomarker assay development will be destroyed no later than 15 years after the final Clinical Study Report has been completed.

However, the storage period will be in accordance with the Institutional Review Board or Ethics Committee (IRB/EC)–approved Informed Consent Form and applicable laws (e.g., health authority requirements).

When a patient withdraws from the study, samples collected prior to the date of withdrawal may still be analyzed, unless the patient specifically requests that the samples be destroyed or local laws require destruction of the samples. However, if samples have been tested prior to withdrawal, results from those tests will remain as part of the overall research data.

Data arising from sample analysis, including data on genomic variants, will be subject to the confidentiality standards described in Section 8.4.

Given the complexity and exploratory nature of exploratory biomarker analyses, data derived from these analyses will generally not be provided to study investigators or patients unless required by law. The aggregate results of any conducted research will be available in accordance with the effective Sponsor policy on study data publication.

